#### 2.2 SECONDARY OBJECTIVES AND OUTCOME MEASURES

• Concordance level between Medipin and standard care device (10g monofilament) for real-world diagnosis of diabetic neuropathy will be determined. However, this is not a true 'quest' for concordance since the two devices are not designed to detect the same underlying nerve damage pathologies. Table 2 below outlines the different outcomes that may be had with the two diagnostic devices.

#### Table 2, Overview of comparison between two neuropathy tests

Test result	Medipin: patient reaction	Medipin: patient reaction absent
	present	
10g monofilament*: patient reaction present	No sign of neuropathy	Only small fibre neuropathy
10g monofilament*: patient reaction absent	Only large fibre neuropathy	Both small and large fibre neuropathy

\*Either dorsal test result or plantar test result, and scored accordingly since sum of multiple applications.

- Evaluation of feasibility that a 10-point/cm visual analogue scale (as instructed by manufacturer) can be applied for Medipin in relation to degree of neuropathy, as opposed to standard yes/no quantification. A three-option scoring system (sharp sensation, dull sensation, absence of sensation) applied earlier with pinprick testing will also be recorded (McNeely et al, 1995).
- Relative performance/concordance achieved with 10g monofilament depending on number of tests and locations included in the assessment. This will be application of the monofilament 4x on the dorsal part of the hallux versus application once on five locations on the plantar side of the foot.

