The use of a pinprick has been advocated in the past and utilized in research studies (Abbott et al,2002; Boulton et al 2008). In those studies, it was shown that inability to perceive the pinprick challenge is significantly associated with a risk of developing ulcers. However, the test does not tend to feature in current NHS guidance on screening for DN. One reason may be that in the past very rudimentary or home-made pinprick device were utilized in the absence of a fit-for-purpose device. Unlike with testing for large fibre nerve damage using the reusable monofilament device, testing for small fibre damage requires more force and therefore should always be conducted using a single use disposable device. Devices like Medipin and also Neurotips (the latter being twice the price per unit compared to the former) meet those criteria. To illustrate past suboptimal practice, in one paper by Smieja et al (1999) the following approach was taken: "Pinprick sensation was tested with a sterile or unused safety pin over the plantar aspect of the distal first, third, and fifth toe of each foot with the stimulus applied once per site. Patients were asked to identify when they felt a sensation, and whether it was sharp or dull. Findings were scored as sharp, dull, or absent for each site".

Taken together, there is a lack of evidence concerning the use of affordable and easy-to-apply devices to diagnose small fibre DN in a real-world community setting. This study will determine the prevalence of small nerve damage using the Medipin device, and compare this to large fibre nerve damage as measured with a 10g monofilament device. Two approaches for monofilament testing will be taken, to take into account a) the variability in standard NHS practice and literature around number and locations tested b) the dorsal approach taken with the Medipin device.

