#### 8.2 SAMPLE SIZE CALCULATION

Since Medipin and monofilament do not assess the same nerve types, a true concordance study cannot be conducted. Hence a sample size is calculated for the prevalence of diabetic neuropathy being present. For the sake of a sample size calculation the assumption is that both tests will detect diabetic neuropathy in a conservative 10% of the sampled population. In the literature a ~20% prevalence of diabetic neuropathy in diabetics is reported but many of these reports are from nearly 30 years ago and therefore a more modest percentage is assumed here. Since it is not expected that the concordance will be high due to the different fibres being tested, calculation of a sample size with sufficient power based on a hypothetical concordance rate is not included here.

Using an online calculator, https://sampsize.sourceforge.net/iface/, with the predetermined criteria of a population of 160,000, 95% confidence interval, and precision of 5%, the required sample size is 139 patients.

Subject to submission of an amendment and appraisal of how patient recruitment into the initial cohort fares, we would like to extend the study to detect 2.5% precision. Again assuming 10% prevalence (which will be reviewed once initial 139 patients have been recruited), 95% confidence interval, and the stricter 2.5% precision, a revised new total of 552 patients will be required.

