#### 8.4 SECONDARY OUTCOME STATISTICS

Evaluation of feasibility that a (Likert) scale can be applied for Medipin in relation to degree of neuropathy, as opposed to standard yes/no quantification and no sensation/dull sensation/sharp sensation distribution. For this, descriptive statistics will be used to present how results are distributed amongst these three outcome modalities. Mann-Whitney U-test will be used to compare median 10-point score between those with present and absent DN respectively (ie yes/no groups), to determine if the median value differs. Similarly, Kruskall-Wallis test will be used to compare median score between the three groups of no sensation/dull sensation/sharp sensation.

Concordance between Medipin and 10g monofilament test results. The binary outcome , DN present or absent, will be used to conduct concordance and distribution comparisons. Cohen's Kappa value will be calculated to assess level of concordance. McNemar's test for paired data will be used to compare distribution of outcomes between Medipin and each 10g monofilament procedure outcome.

Relative performance/concordance achieved with 10g monofilament depending on number of tests and locations included in the assessment. As above for concordance measurement between Medipin outcome and respective 10g monofilament outcomes, the same test is conducted to compare the two different 10g monofilament diagnostic test procedures.

The patient's age, years of diabetes, smoking status, blood pressure medication and diabetes medication, foot malformations, general quality of life (EQ-5Q-DL), and MNSI symptom questionnaire score are primarily used to define the cohort on which the DN screening has been conducted. Parameters collated at the clinic visit will be recorded and presented in a tabulated format. No identifiable data will be presented, only averages and totals.

However, binary logistic regression may be applied to evaluate if any parameters are associated with Medipin positive tests, with the the Medipin result being the dependent variable. Likewise, this regression analysis can also be used with either of the monofilament test outcomes as the dependent. This will then allow comparison of variables associated with small fibre and large fibre screening. This type of analysis may only be feasible with the potential larger sample size outlined in Section 8.2 of this protocol. Odds ratios (logistic) will be expressed as Beta with 95% confidence intervals.

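### Table 2 names every Medipin/monofilament disagreement as a fibre-specific neuropathy, which this design cannot establish and which the Table 6 cut-offs can contradict

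*Protocol*

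**What the plan says.** Section 2.2 makes concordance between Medipin and the 10g monofilament a secondary objective, and notes that "the two devices are not designed to detect the same underlying nerve damage pathologies". Table 2 then crosses the two binary results. The two discordant cells are named "Only small fibre neuropathy" (Medipin not felt, monofilament felt) and "Only large fibre neuropathy" (the reverse). The footnote leaves open which monofilament result is used: "Either dorsal test result or plantar test result, and scored accordingly since sum of multiple applications".

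The same reading appears elsewhere. Section 1 announces: "This study will determine the prevalence of small nerve damage using the Medipin device". Section 8.4, on an optional logistic regression of each test result, says: "This will then allow comparison of variables associated with small fibre and large fibre screening".

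Table 6 (section 8.3) sets the binary cut-offs:
- **Medipin:** positive if there is no sensation in either foot or in both.
- **Dorsal monofilament:** scored over both feet, maximum 8; positive at 3 or lower.
- **Plantar monofilament:** scored over both feet, maximum 10; positive at 8 or lower.

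Section 8.4 plans Cohen's kappa and McNemar's test for Medipin against each monofilament procedure, and the same comparison between the two monofilament procedures.

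**The concern.** A fibre-specific name for a discordant pair assumes that disagreement has one cause. Two bedside tests can also disagree because of a missed response, a false alarm, a different site, a different number of attempts or a different cut-off. The protocol acknowledges some of this. Section 1 says the monofilament tests large fibres predominantly, that its result varies with the operator, prior use of the device and the weather, and that one-site testing had a sensitivity of around 50% in studies using ulcer history as the reference.

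The visit schedule (section 5.2) contains no objective test of fibre type and no repeat Medipin application, so nothing collected can separate these causes. What is at stake is the reading of the study's distinctive result. A count of patients positive on Medipin alone would be presented as small-fibre disease that the monofilament misses, when the data show only that two tests disagreed.

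**Working it through.** **1. The plan's own sample size.** Section 8.2 uses 10% positive, 95% confidence and a population of 160,000. With n0 = 1.96² × 0.10 × 0.90 / d² and the finite-population correction n0 / (1 + (n0 − 1)/160,000):
- d = 5%: n0 = 138.29, corrected 138.17, rounded up to 139. This matches "precision of 5%, the required sample size is 139 patients".
- d = 2.5%: n0 = 553.17, corrected 551.27, rounded up to 552. This matches "stricter 2.5% precision, a revised new total of 552 patients will be required".

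The 139 and the 10% are carried forward.

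**2. A false label with no random error.** Inputs are the scoring in section 5.3 and the cut-offs in Table 6. Take a patient who feels nothing on one hallux and has normal sensation on the other.
- Dorsal monofilament: 4 × 0 + 4 × 1 = 4 of 8. This is 3.5 or higher, so DN absent.
- Medipin: one foot without sensation, so DN present.
- Table 2, using the dorsal result: small-fibre only.

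None of the four monofilament applications on the affected foot was felt. The label comes from summing one test over both feet while the other counts either foot.

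If the loss also covers all five plantar sites of that foot (an added assumption), the plantar score is 5 × 0 + 5 × 1 = 5 of 10, so DN present. The same patient then moves to the cell for both fibre types. Because the footnote allows either result, the fibre label can depend on which one is chosen.

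**3. Other differences between the tests.** Medipin is applied once per foot on the dorsal hallux. The dorsal monofilament is applied four times per foot. A plantar site with no response is tried twice more before being recorded as not felt.

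**4. Illustration with test error.** The protocol gives no error rates for Medipin, so these are assumptions. Suppose one common nerve loss with prevalence π = 10%, read by two tests with the same sensitivity (Se) and specificity (Sp) and with errors independent given true status. Then

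q = P(Medipin positive, monofilament negative) = π·Se·(1 − Se) + (1 − π)·(1 − Sp)·Sp.

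The expected count is 139q. By symmetry the large-fibre-only cell has the same expectation. The share of Medipin positives labelled small-fibre only is q / [π·Se + (1 − π)(1 − Sp)].

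| Se / Sp (assumed) | q | Expected in each discordant cell | Share of Medipin positives |
|---|---|---|---|
| 95% / 99.5% | 0.00475 + 0.00448 = 0.0092 | 1.3 | 0.0092/0.0995 = 9% |
| 90% / 99% | 0.00900 + 0.00891 = 0.0179 | 2.5 | 0.0179/0.0990 = 18% |
| 80% / 98% | 0.01600 + 0.01764 = 0.0336 | 4.7 | 0.0336/0.0980 = 34% |
| 90% / 95% | 0.00900 + 0.04275 = 0.0518 | 7.2 | 0.0518/0.1350 = 38% |

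In each row no patient has a fibre-specific condition, yet both fibre-specific cells are expected to be occupied.

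**5. What the planned tests can show.** McNemar's test compares the two positive rates. Under the equal-error cases above, the exact version rejects in about 0.1%, 0.9%, 2.1% and 2.7% of studies, in table order. It would normally find no difference, correctly, while the cells keep their fibre names. Kappa measures agreement only. Neither statistic speaks to why a pair disagrees.

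**The case against.** Several points on the other side stand.

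- **Table 2 is an overview.** Section 2.2 introduces it as possible outcomes and says this is not a true test of concordance. Table 6 and section 8.4 classify patients only as DN present or absent, and no test of the fibre labels is planned. This limits the reach of the point, but the labels still sit under a secondary objective and recur in sections 1 and 8.4.
- **The pragmatic design explains the missing reference test.** That is a fair reason not to have one. It is not a reason to draw a conclusion that needs one.
- **The symptom questionnaire separates small- and large-fibre items (Appendix 4).** These are self-reported symptoms. Section 8.4 uses the score mainly to describe the cohort and nowhere uses it to check the Table 2 cells.

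Three stronger readings are tempting, and the protocol does not support them.

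- A reader might infer that a small-fibre finding would be declared even if no fibre difference existed. No rule makes one patient, or any number, in a cell establish such a finding, and McNemar's test rejects rarely in the cases above.
- A reader might infer that patients would receive a fibre-type diagnosis. Section 3.1 says only that the GP is notified of signs of neuropathy, and the case report form records raw responses with no fibre-type field.
- A reader might infer that section 8.4 interprets kappa by fibre type. It does not. The expectation of low concordance because of different fibres is in section 8.2, where it explains why no concordance-based sample size was calculated.

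**Conclusion.** Wrong as written. The labels in the two discordant cells claim more than the design can show, and Table 6 yields at least one patient profile for which the small-fibre-only label contradicts the monofilament responses on the affected foot. That example needs no assumption about error rates; it needs only the dorsal result to be the one used.

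The size of the effect from test error is illustrative: about 1 to 7 of 139 patients in each discordant cell for sensitivity/specificity from 95%/99.5% to 90%/95%. This rests on 10% prevalence, a single common nerve loss, and equal, independent errors. Error rates outside this range, unequal errors or correlated errors would change the counts.

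The point concerns a secondary objective and its interpretation. The primary result, the percentage positive on each test, is unchanged.

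**What to change.** 1. Rename the Table 2 cells by what is observed: *negative on both*, *Medipin positive only*, *monofilament positive only*, *positive on both*.
2. Add one sentence stating that discordance alone does not establish fibre type, because the tests also differ in site, repeats and cut-off and no fibre-type reference is used.
3. Reword the section 1 sentence on small nerve damage and the section 8.4 sentence on small- and large-fibre screening so that they refer to Medipin-positive and monofilament-positive results.
4. Optionally, show the already planned plantar-versus-dorsal monofilament kappa beside the Medipin-versus-dorsal kappa, as descriptive context only.

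The comparison in item 4 should not become a gate for a fibre-specific conclusion. Suppose there is no fibre difference, both monofilament tests have 90% sensitivity and 99% specificity, and Medipin is merely less specific (all assumed). A rule that required Medipin-dorsal discordance to exceed plantar-dorsal discordance, with a bootstrap 95% interval above zero, would then allow a fibre-specific reading in roughly a third of trials at Medipin specificity 95% and roughly four fifths at 90%.

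The cost is wording in three places, with no new data, visits or patients. The protocol gives up the fibre-specific language, but can still report how many patients each test flags alone.

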#### 3 INVESTIGATIONAL PLAN

#### 3.1 TRIAL DESIGN AND TIMELINE

Prospective, single-centre, controlled, non-randomised, prospective evaluative diagnostic study.

Table 3 shows the anticipated timeline for the study. For this study, appropriately trained staff will conduct the Medipin and monofilament tests.

During the study period, all patients can continue to be managed and receive their standard treatment regime by their usual clinical team. Therefore, management of participants' diabetes is not affected by participating in this present study. If signs of diabetic neuropathy are identified then the patient's GP will be notified by means of a GP notification letter. The regular GP and/or diabetes practice nurse can then decide the next course of action in relation to those findings, should they deem this necessary.

#### Table 3, Anticipated study timeline

Month	Setup	Cohort	Analysis
Mar 2023	Submission to		
	NRES and HRA		
	NIHR portfolio adoption		
May 2023	HRA and Trust approval	Start recruitment	
Jan 2024		Finish all recruitment	
Mar 2024			Finalise analysis & report

#### 4 PARTICIPANTS

#### 4.1 TRIAL PARTICIPANTS & LOCATIONS

Patients will be recruited from the adult population managed in one of 13 different GP practices, see Table 4. The GP practices will act as Patient Identification Centres, and the study activities will take place in the clinic spaces of North Cumbria Integrated Care NHS.

Table 4,	List of	participating	GP	practices
----------	---------	---------------	----	-----------

ODS CODE	name	POSTCODE	patient list (Jan2023)
A82016	Carlisle Healthcare	CA1 1DG	37516
A82047	James Street Group Practice	CA14 2DL	32999
A82044	Fellview Healthcare	CA28 7QE	24021
A82020	Eden Medical Group	CA2 7AJ	16330
A82041	Lowther Medical Centre	CA28 7RG	9971
A82045	Wigton Group Medical Practice	CA7 9QD	8980
A82654	Warwick Square Group Practice	CA1 1LB	7777
A82055	Aspatria Medical Group	CA7 3HH	6869

#### MANDARIN protocol v1.1 dd 20Apr2023

A82024	Seascale Health Centre	CA20 1PN	5878
A82038	Temple Sowerby Medical Practice	CA10 1RW	4882
A82058	Queen Street Medical Practice	CA28 7BA	4372
A82037	Silloth Group Medical Practice	CA7 4AH	4328
A82631	Court Thorn Surgery	CA4 0HP	3690

Identification of potentially eligible patients will be done by the Investigator/GP. Therefore, the patient will be approached initially by the clinical team caring for them. An invite letter and patient information sheet is sent out to the eligible patients and they then return a reply slip via Freepost if they are interested in participating. The patient is then contacted – they will have indicated how they prefer to be contacted on the reply slip – and they will attend a one-off study visit. The researchers will obtain written informed consent from the patients after talking them through the patient information sheet. Then the tests for diabetic neuropathy and questionnaires will be conducted.

#### 4.2 INCLUSION & EXCLUSION CRITERIA

Inclusion criteria:

- Adult patients aged  $\geq$  18 years
- Patients with type I or type II diabetes mellitus

#### Exclusion criteria:

- Aged < 18 years
- Any reasons for the patient being unable to follow the protocol, including lack of mental capacity to consent to taking part in the study (examples include dementia, severe learning disability). Pure language barriers, eg lack of spoken English or eg deafness/blindness, are not an exclusion criterion.
- The patient has concurrent (medical) conditions that in the opinion of the investigator may compromise patient safety or study objectives (examples include receiving palliative care, active cancer treatment, patient immobile)
- Amputation of a lower limb
- Confirmed and ongoing wound / ulcer located on the foot

#### 5 STUDY PROCEDURES

#### 5.1 INFORMED CONSENT

Before being recruited to the clinical evaluation, the patient must have consented to participate, after the nature, scope and possible consequences of the evaluation have been explained in an understandable form. An initial invite letter and patient information leaflet will be provided to the patient via post. If patients are interested, they then return a reply slip and during the study visit the patient will provide written informed consent. Consent to take part in this research is obtained from adult patients, where they possess mental capacity.

During the consent procedure the following information will be outlined in writing, which will also be relayed verbally: a) The evaluation involves research, a description of the aims of the evaluation and how

it will be organised and the expected duration of the patient's participation; b) Any potential risks and benefits of taking part; c) The freedom to ask for further information, and to withdraw from the study, at any time; d) The extent to which confidentiality of records identifying the patients will be maintained and that the Regulatory Authorities may inspect the records.

The staff will be trained in obtaining informed consent as part of professional development, members of staff involved in the consent process will also have current ICH Good Clinical Practice training (even though this officially does not fall under the remit of Good Clinical Practice requirements).

#### 5.2 STUDY PROCEDURES

After completing informed consent, information on relevant clinical parameters and demographics will be collected. See Table 5 for an overview of the activities conducted at the single research visit. The Medipin assessment is an added investigation, whereas the other activities are all part of a diabetes (foot) review.

Table 5, C	Overview d	of study	activities	for study	participants	at single stud	ly visit.
------------	------------	----------	------------	-----------	--------------	----------------	-----------

Activity (in this order)	Reference for rationale
Diabetes status and history	
Patient demographics	
General quality of life questionnaire (EQ-5D-5L)	Herdman et al, 2011
Michigan Neuropathy Screening Instrument symptom	Moghtaderi et al, 2006
10g Monofilament test plantar side, five plantar	GP notebook online resource
locations on both left and right foot	Gr Hotebook online resource
10g Monofilament test: four applications on dorsal side of hallux, proximal to toenail, on both left and right foot	Canadian Journal Diabetes, 2018
Medipin test: one application on dorsal side of hallux, proximal to toenail, on both left and right foot	Boulton et al, 2008

#### 5.3 DESCRIPTION OF TESTS FOR DN

#### 10g Monofilament test plantar side, multiple locations

https://gpnotebook.com/simplepage.cfm?ID=x2020063010498191128. Scoring system based on five sites on each foot = 10 sites; if score of 8 or less then indicative of neuropathy (Baker 2011; Boulton et al 2008)

#### MANDARIN protocol v1.1 dd 20Apr2023

- Apply the filament to a sensitive area of skin (e.g. the forearm) so that the patient is aware of the sensation they are supposed to feel.
- Test 5 sites\* on both feet:
  - ✔ Plantar surface of the hallux and 3rd toe
  - ✓ 1st, 3rd and 5th metatarsal heads
  - \*If callus is present at any of the sites then test at the nearest non-calloused area.
- · Ask the patient to close their eyes and say 'yes' every time that they feel you touch the skin on the foot
- Place the monofilament at 90° to the skin surface
- Slowly push the monofilament until it has bent ~ 1cm (don't jab)
- Hold the monofilament in this position for 1-2 seconds, then slowly release the pressure until the monofilament is
- straight
  Remove contact from the skin
- If the patient does not respond, repeat the test at the site twice. If there is still no response, record as a negative response
- Maximum score 10. A score of 8 or less indicates neuropathy
- Replace monofilament after 500 uses (approximately 6 monthly frequent testing, yearly infrequent testing)

